2.5. Safety Outcome Measures

Safety will be assessed through the evaluation of adverse events (AEs), vital signs (temperature, heart rate, blood pressure, and respiratory rate), physical examinations (including neurological examinations), ECGs and clinical laboratory evaluations (hematology evaluations, chemistry panel, and urinalyses). Subjects will also be assessed at Screening and at the EOT visit, prior to Rezafungin for Injection dosing, with a thorough neurologic evaluation to assess for signs and symptoms of tremor, ataxia, and peripheral neuropathy. Adverse events will be graded for severity using the National Cancer Institute Common Terminology Criteria for Adverse Events (CTCAE) system version 5.0.

2.6. Population Definitions

The following analysis populations will be evaluated and used for presentation and analysis of the data:

- The intent-to-treat (ITT) population will include all randomized subjects.
- The safety population will include all subjects who received any amount of the study drug. Safety assessments will be performed on the safety population. Subjects who receive the wrong study drug for their entire course of study drug will be analyzed in the treatment group based on the drug received. Subjects who receive the wrong study drug for part of their course of study drug will be analyzed in the treatment group based on majority of (i.e., most frequent) doses received.
- The mITT population will include all subjects who had a documented *Candida* infection based on Central Laboratory evaluation of a blood culture or a culture from a normally

sterile site obtained ≤ 4 days (96 hours) before randomization and received ≥ 1 dose of study drug.

- The clinically evaluable (CE) population will include all subjects in the mITT population who also met inclusion criterion #4, did not meet exclusion criteria #1, #2, and #5, had a response other than indeterminate for both mycological and clinical response as assessed by DRC at Day 14 in the protocol specified window of Day 14 \pm 1 day (subjects with invasive candidiasis documented by radiologic/imaging evidence also must have a radiological response by DRC other than indeterminate), and did not receive a concomitant antifungal that could confound the assessment of the global response at Day 14.
- The Pharmacokinetic (PK) population will include all subjects who received any amount of study drug and have at least one blood sample with measurable concentrations.

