13.5 Safety Analyses

All safety analyses will be conducted in the Safety population and will be summarized by study drug actually received.

A TEAE is defined as an AE that occurs during or after the first dose of study drug up through the Follow-up visit (Days 52–59). An overall summary of AEs will be provided by treatment group. The incidence of TEAEs will be presented by SOC and Preferred Term (PT); SOC, PT

and relationship to the study drug administration; and SOC, PT, and CTCAE grade (version 5.0). Tables of any TEAE resulting in discontinuation of study drug and SAEs will also be provided. A table of TEAEs of coronavirus will be presented by PT and a listing of all TEAEs in subjects with COVID-19 (medical history or TEAE) will be provided. Depending upon the number of subjects diagnosed with COVID-19, a summary of TEAEs by SOC and PT may be provided.

Descriptive statistics for clinical laboratory test results (hematology and chemistry) will be presented for all study visits. The change from baseline to each post-baseline visit and to the overall worst post-baseline value will be summarized by treatment group. Laboratory values will be graded using CTCAE version 5.0 and shift tables will be provided. Liver enzymes will be classified as > ULN, >3×, >5× and >10×ULN and the number and percentage of subjects with any post-baseline value in one of the categories will be presented by study drug.

Descriptive statistics of vital sign parameters will be presented by treatment group and study visit, as well as the change from baseline at each study visit. Potentially clinically significant (PCS) values will be defined in the SAP and the number and percentage of subjects with a PCS value will be summarized by treatment group for the worst-post-baseline value.

Descriptive statistics of ECG parameters will be presented by treatment group and will include change from baseline.

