1.2. Synopsis of Study Design

This is a Phase 3, multicenter, prospective, randomized, double-blind, efficacy and safety study of intravenous (IV) Rezafungin for Injection (laboratory code: CD101) versus an active comparator regimen of caspofungin (IV) followed by optional oral fluconazole step-down therapy in subjects with candidemia and/or invasive candidiasis (IC). Subjects will receive either IV Rezafungin for Injection or IV caspofungin, randomized in a 1:1 ratio. Subjects can be switched to oral step-down treatment by the Investigator after ≥ 3 days of IV treatment (or the minimum duration of IV therapy advised by the site's national/regional/local guidelines, whichever is greater) if they meet the oral step-down therapy criteria (as described in the Protocol Section 8.2.3.2).

Subjects randomized to receive Rezafungin for Injection:

Subjects will receive a loading dose of Rezafungin for Injection 400 milligram (mg) in Week 1, followed by 200 mg once weekly for a total of 2 to 4 doses. To maintain the blind, subjects will also receive placebo for caspofungin IV, which will be administered on Days 2-7, Days 9-14 and during the optional dosing period on Days 16-21 and Days 23-28, or will receive daily placebo for oral step-down therapy (first eligibility on Day 4 or later as advised by a site's national/regional/local guidelines), which will be administered every day including rezafungin infusion days.

Subjects randomized to caspofungin:

Subjects will receive a total treatment of ≥ 14 days beginning with a single caspofungin 70 mg IV loading dose on Day 1 followed by caspofungin 50 mg IV once daily with the option to continue treatment ≤ 28 days. After ≥ 3 days (or the minimum duration of IV therapy advised by the site's national/regional/local guidelines, whichever is greater) of caspofungin treatment, subjects who meet the step-down therapy eligibility criteria may

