4.5. Analysis of Safety Data

All safety analyses will be conducted in the Safety population. Subjects who receive the wrong study drug for their entire course of study drug will be analyzed in the treatment group based on the drug received. Subjects who receive the wrong study drug for part of their course of study

drug will be analyzed in the treatment group based on majority of (i.e., most frequent) doses received.

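### Placing mixed-exposure subjects in safety groups by dose count is a poor proxy for rezafungin exposure, because rezafungin is weekly, caspofungin is daily and a dose is not defined

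*SAP*

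**What the plan says.** Protocol 13.5 says that safety data "will be summarized by study drug actually received" and gives no rule for a subject who received both drugs. The SAP supplies one. Section 2.6 says that a subject given the wrong drug for part of the course is "analyzed in the treatment group based on majority of (i.e., most frequent) doses received". Section 4.5 repeats it for all safety analyses: "Subjects who receive the wrong study drug for part of their course of study" drug are placed "based on majority of (i.e., most frequent) doses".

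The two regimens are described in SAP 1.2. Rezafungin is a loading dose in Week 1, "followed by 200 mg once weekly for a total of 2 to 4 doses". The comparator is a loading dose "followed by caspofungin 50 mg IV once daily", and for the caspofungin arm "Subjects will receive a total treatment of ≥ 14 days". Between its weekly infusions the rezafungin arm receives "placebo for caspofungin IV, which will be administered on Days 2-7, Days 9-14", and likewise in the optional period, unless the subject has switched to oral placebo.

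Neither document says whether a placebo infusion or an oral capsule counts as a dose under the rule, or what happens when the counts are equal.

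**The concern.** A majority-of-doses rule is a reasonable summary of exposure when both arms dose at about the same frequency. Here one arm gives an active infusion every seventh day and the other every day. One rezafungin infusion counts the same as one daily caspofungin infusion, although its effect on exposure lasts far longer. Protocol 4.6 gives a terminal half-life of 127 to 146 hours. Protocol 4.8.3 asks for sun precautions for five half-lives after the last dose.

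At stake are the tables by treatment group, above all the adverse events of special interest in SAP 4.5.1: infusion intolerability, phototoxicity, and ataxia, neuropathy and tremor. Protocol 12.7 links the last two categories to findings with rezafungin. When events are rare, moving one exposed subject with an event from one column to the other can change what the table shows.

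**Working it through.** The documents state no figure for this rule, so there is nothing to reproduce. The check applies the rule to the dosing schedule.

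**Inputs.** Rezafungin active infusions fall on Days 1, 8, 15 and 22 (Protocol Table 3; SAP Appendix 4), that is 2 on a 14-day course and 4 on a 28-day course. Caspofungin is active every day, so 14 or 28 infusions if the subject stays on IV therapy. The half-life is 127 to 146 hours.

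**Two readings.** (a) Only active doses count. (b) Every daily infusion counts for the arm it was prepared for, placebo included.

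**Single cases, IV-only courses** (rezafungin count versus caspofungin count):

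| Case | (a) Active only | (b) Placebo counted |
|---|---|---|
| Caspofungin subject, rezafungin in error on both weekly days, 14 days | 2 v 14 − 2 = 12: caspofungin | 2 v 12: caspofungin |
| Same, all four weekly days, 28 days | 4 v 28 − 4 = 24: caspofungin | 4 v 24: caspofungin |
| Rezafungin subject, both active doses, 3 caspofungin doses on placebo days, 14 days | 2 v 3: caspofungin | 14 − 3 = 11 v 3: rezafungin |
| Same, with 2 caspofungin doses | 2 v 2: tie, no rule | 12 v 2: rezafungin |
| Same, with 1 caspofungin dose | 2 v 1: rezafungin | 13 v 1: rezafungin |
| Rezafungin subject on the wrong arm from Day 8, 14 days | 1 v 7: caspofungin | 7 v 7: tie, no rule |

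On reading (a), a rezafungin subject with every active dose moves once the erroneous caspofungin doses exceed the rezafungin doses: 2 + 1 = 3 on a 14-day course and 4 + 1 = 5 on a 28-day course.

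**All single-run errors.** Take every unbroken run of wrong-arm days on an IV-only course, for either randomized arm, and keep those that give at least one active dose of each drug. For 14 days this is 98 + 62 = 160 patterns; for 28 days, 399 + 321 = 720.

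| Course, reading | To caspofungin | To rezafungin | Tie |
|---|---|---|---|
| 14 days, (a) | 74 + 59 = 133 (83%) | 12 + 1 = 13 | 12 + 2 = 14 |
| 14 days, (b) | 21 + 27 = 48 (30%) | 69 + 27 = 96 | 8 + 8 = 16 |
| 28 days, (a) | 306 + 311 = 617 (86%) | 71 + 6 = 77 | 22 + 4 = 26 |
| 28 days, (b) | 98 + 202 = 300 (42%) | 286 + 104 = 390 | 15 + 15 = 30 |

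These are counts of possible patterns. They are not probabilities of an error.

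**Persistence.** With simple one-half-life decay, the fraction of a dose left after 7 days (168 hours) is 2^(−168/127) = 0.40 to 2^(−168/146) = 0.45. Five half-lives are 5 × 127 = 635 hours (26 days) to 5 × 146 = 730 hours (30 days).

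**Oral step-down.** The 2 versus 12 case assumes none. With the earliest permitted switch, on Day 4, the same subject has caspofungin only on Days 2 and 3. That is 2 v 2, a tie, if only caspofungin counts. It is 2 v 2 + 11 = 13 if the fluconazole doses of Days 4 to 14 count too.

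**The case against.** The strongest reply is that a dose need not mean an active dose. Protocol 8.0 speaks of study drug given every 24 hours in the rezafungin arm, and the synopsis places the last required dose of study drug on Day 14, which is placebo in that arm. On that reading the three-dose example fails (11 versus 3), and most mixed patterns stay under rezafungin. This stands. A reader might infer that the rule always takes rezafungin-exposed subjects out of the rezafungin group. The documents do not support that: even with active doses only, 13 of the 160 patterns stay under rezafungin and 14 tie.

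Second, the rule applies only after a dispensing error. Preparation is in the hands of unblinded pharmacy staff with a pharmacy monitor (Protocol 6.5 and 8.6). No error count is given, and it may be zero. This stands too. Reading 83% as a share of subjects would be wrong.

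Third, SAP 4.1.2, 4.2.1 and 4.5.1 already plan listings of deviations, IV doses and events of special interest. A mixed-exposure subject could be traced through them, but they leave the subject in the same column of the tables.

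Fourth, one might infer that the SAP contradicts Protocol 13.5. It does not: it adds a rule where the protocol has none.

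**Conclusion.** The point holds as a minor one. Dose count is a poor measure of rezafungin exposure in this design, and the rule is incomplete because it neither defines a dose nor resolves ties.

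One result does not depend on how placebo infusions are counted: on an IV-only course, a caspofungin subject who received the whole weekly rezafungin schedule in error is tabulated under caspofungin (2 v 12, or 4 v 24). The wider imbalance is conditional on counting active doses only. If placebo infusions count, it mostly disappears, though 48 of the 160 fourteen-day patterns still go to caspofungin.

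The conclusion rests on IV-only courses and, for the pattern counts, on a single unbroken run of wrong-arm days. The number of subjects affected is unknown, probably few in a trial of about 218, and possibly none. Pooled adverse event rates should barely move. The exposed place is a rare event of special interest. Efficacy is unaffected, because it is analyzed as randomized (SAP 4.3).

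**What to change.** In SAP 2.6 and 4.5, replace the majority-of-doses sentence with this rule: for safety, any subject who received at least one active rezafungin dose is tabulated under rezafungin, and all other dosed subjects under caspofungin. Add a separate listing of mixed-exposure subjects showing the drugs and dates received. None of the 160 fourteen-day patterns would then fall under caspofungin. Naming the active dose also removes both the tie and the question of what counts.

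The cost is one sentence in two places and one listing, with no new data. SAP 1.1.1 provides for such a change by amendment before database lock. The downside is an opposite misplacement: a subject with mostly caspofungin and a single rezafungin dose would carry all events, including caspofungin-related ones, into the rezafungin column. For the safety assessment of a new drug that is the cautious direction, and the listing would show which subjects are concerned.

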7.4.2 Early Discontinuation from Study Drug Administration

For subjects who prematurely discontinue study drug (i.e., before the anticipated full course of study drug therapy required for effective treatment of candidemia and/or invasive candidiasis), EOT assessments should be performed on the day of discontinuation. For premature study drug discontinuation, Day 14 efficacy assessments should also be performed at EOT, except when the subject is believed to be a clinical cure, then the efficacy assessments should still be performed at the Day 14 visit to ensure there is no relapse between EOT and Day 14. All safety assessments and assessment of mortality should be done for subjects who discontinue study drug early. The reason for premature discontinuation of study drug administration should be recorded on the appropriate page(s) of the eCRF. Reasons for withdrawal from study drug may include, but are not limited to:

- Cultures negative for *Candida* spp.
 - Blood culture is positive for yeast at enrollment, but the final local blood culture results conclude the yeast is not *Candida* spp.
 - Subject is enrolled based on a rapid IVD test positive for *Candida* spp., but final local blood culture results from Screening or tissue/fluid culture results from a normally sterile site are negative for *Candida* spp. (withdrawal not required but based on the Investigator's discretion)

- Safety
 - Subject unable or unwilling to continue or informed consent withdrawn
 - Occurrence of an AE that, in the opinion of the Investigator, warrants the subject's permanent discontinuation from study drug therapy. This includes development of a clinically significant laboratory abnormality that requires discontinuation from study drug (IV and IV/oral) therapy. In the event of discontinuation from study drug therapy due to the occurrence of an AE, the study site should notify the Medical Monitor as soon as possible
 - Suspected or confirmed pregnancy or nursing during the study drug administration period
- Excluded types of invasive candidiasis

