13.1 Analysis Populations

The analysis populations are defined for this study as follows:

- The intent-to-treat (ITT) population will include all randomized subjects, regardless of whether the subject receives study drug.
- The Safety population will include all subjects who received any amount of study drug.
- The mITT population will include all subjects who had documented *Candida* infection based on Central Laboratory evaluation of a culture from blood or another normally sterile site obtained ≤ 4 days (96 hours) before randomization and received ≥ 1 dose of study drug.
- The clinically evaluable (CE) population will include all subjects in the mITT population who also met inclusion criterion #4, did not meet exclusion criteria #1, #2, or #5, had an assessment of both mycological and clinical response at Day 14 in the window of Day 14 (± 1 day) (subjects with invasive candidiasis documented by radiologic/imaging evidence also must have an assessment of radiologic response), and did not have any other factor that could confound the assessment of the global response at Day 14.
- PK Analysis Population will include all Rezafungin for Injection subjects with at least 1 plasma sample obtained for PK analysis.

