If a subject discontinued the study medication prior to Day 14 and the global response at the EOT visit is failure, the global response at Day 14 for that subject is failure. If study drug was stopped early because the PI thought the subject was a clinical cure, the subject must be assessed during the Day 14 window. If the subject did not have the assessment, the global response for that subject at Day 14 is indeterminate.

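### As written, the CE population can exclude early failures while keeping early-stopping cures seen on Days 13–15, because SAP 2.6 does not say how its window, antifungal and component rules treat them

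*SAP*

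**What the plan says.** **CE membership.** SAP 2.6 requires that a CE subject "had a response other than indeterminate for both mycological and clinical response as assessed by DRC at Day 14 in the protocol specified window" (Days 13–15). Subjects with imaging-documented invasive candidiasis also need a determinate radiological response. The subject must be one who "did not receive a concomitant antifungal that could confound the assessment of the global response at Day 14". Protocol 13.1 differs in two places: the subject "had an assessment of both mycological and clinical response at Day 14 in the window of Day 14" and "did not have any other factor that could confound the assessment of the global response at Day 14". The protocol thus asks for an assessment, the SAP for a response.

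**Timing after early discontinuation.** Under Protocol 7.4.2, "EOT assessments should be performed on the day of discontinuation". The same section says that "Day 14 efficacy assessments should also be performed at EOT, except when the subject is believed to be a clinical cure"; for that exception, "then the efficacy assessments should still be performed at the Day 14 visit". Subjects stopped for insufficient effect stay in the study for safety and mortality; that paragraph does not mention efficacy.

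**Failure assigned to Day 14.** SAP 2.2.1 provides that "If a subject discontinued the study medication prior to Day 14 and the global response at the EOT visit is failure", the Day 14 global response is failure. SAP 2.2.3 does the same for the Investigator's clinical response, and makes progression or rescue before a time point a clinical failure from then on. Death by the day of assessment is failure in SAP Tables 2-3, 2-4 and 2-5. A change of antifungal by that day is mycological failure (Table 2-3). Rescue therapy is a failure event in the EMA estimand (Table 2-1).

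**Use.** SAP 4.3.1.1 makes CE the third sensitivity analysis of the EMA primary endpoint.

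**The concern.** When the Day 14 assessment takes place depends on how the subject appears to be doing at discontinuation. A population rule that turns on an assessment between Days 13 and 15 can therefore select on outcome: early failures are seen too soon to qualify, and early-stopping cures are seen at the qualifying visit. The antifungal clause points the same way if rescue treatment, which marks a failure, is also taken as a reason for exclusion.

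A third route is separate from timing. SAP 2.6 needs every required component to be determinate, but Table 2-2 makes a clinical failure a global failure even when mycology or radiology is indeterminate. A global cure has no indeterminate component by definition, so this rule can remove definite failures and never a cure.

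Of the three EMA sensitivity analyses, CE is the only one run outside the mITT population. Losing failures from both arms raises both cure rates and, if the loss is similar, shrinks a true deficit. CE could then seem to support non-inferiority because of how it was assembled.

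**Working it through.** **1. Cases under two readings of SAP 2.6.** *Literal*: an actual assessment is needed in Days 13–15, and rescue counts as confounding. *Carry-forward*: a failure assigned to Day 14 satisfies the window, and rescue is not confounding. Each subject is taken to meet the other CE criteria.

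| Subject | Day 14 result under the SAP | Literal | Carry-forward |
|---|---|---|---|
| Dies on Day 6 | Failure | Out | In |
| Stops on Day 9 as a failure, rescued | Failure | Out | In |
| Stops on Day 9 for an AE; baseline imaging positive, no follow-up imaging | Global failure, radiology indeterminate | Out | Out |
| Failure seen on Day 14, no rescue, components determinate | Failure | In | In |
| Early-stopping presumed cure, confirmed on Day 14 | Cure | In | In |
| Early-stopping presumed cure, not seen in window | Indeterminate | Out | Out |

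The first two rows change with the reading. The third is lost on either.

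**2. The plan's own figure.** The documents give no CE size, power or exclusion rate. The planning basis is Protocol 13.8: 70% global cure in both arms, 20-point margin, one-sided alpha 0.025, 92 mITT subjects per arm.

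- Uncorrected n = 2 × 0.70 × 0.30 × (1.960 + 0.842)² / 0.20² = 82.4 per arm.
- Continuity-corrected n = (82.4/4) × [1 + √(1 + 4/(82.4 × 0.20))]² = 92.1 per arm.
- Continuity-corrected power at 92 per arm = 79.9%, against the stated 80%.

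The plan's figure is reproduced and is not in dispute.

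**3. Effect on CE cure rates.** Let p be the mITT cure rate and g the share of mITT failures left out of CE. With no other exclusions and no indeterminates,

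CE cure rate = p / [p + (1 − p)(1 − g)].

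The documents give no value for g; it is assumed and varied. Example at g = 50%: 0.70/(0.70 + 0.30 × 0.50) = 0.824 and 0.50/(0.50 + 0.50 × 0.50) = 0.667, a difference of −15.7 points.

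True mITT cure 50% (rezafungin) v 70% (caspofungin), with g equal in both arms:

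| g | CE cure rates | CE difference | CE n per arm | Chance CE shows non-inferiority |
|---|---|---|---|---|
| 0 | 50.0% v 70.0% | −20.0 | 92 / 92 | 2.6% |
| 25% | 57.1% v 75.7% | −18.5 | 80.5 / 85.1 | 3.9% |
| 50% | 66.7% v 82.4% | −15.7 | 69.0 / 78.2 | 8.7% |
| 75% | 80.0% v 90.3% | −10.3 | 57.5 / 71.3 | 30.0% |

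CE n per arm is 92 × [p + (1 − p)(1 − g)]. The last column comes from 20,000 simulated trials with an unstratified Miettinen–Nurminen score test; the planned CE interval is stratified. The row g = 0 is the carry-forward reading with no loss through indeterminate components.

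**4. Unequal exclusion.** With 70% cure in both arms, g = 50% on rezafungin and 25% on caspofungin, CE shows 82.4% v 75.7%, a spurious +6.7 points. Reversing the shares reverses the sign.

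**The case against.** The strongest reply is that the SAP asks for a response, not an assessment, and supplies one. Sections 2.2.1 to 2.2.4 assign failure at Day 14 to prior deaths, rescue and EOT failures. SAP 3.8 summarizes efficacy by nominal visit, and Protocol 7.4.2 itself treats the assessment done at EOT as the Day 14 one. Rescue fixes the outcome as failure, so there is little left to confound, and Protocol 8.5 already separates antifungal use for treatment failure from other concomitant use. On this view the first two rows of the case table stay in.

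This is a tenable reading, and it defeats the stronger claim that a reader might infer: that CE certainly drops failures and keeps cures. Failures seen in the window stay in, unless the antifungal or component rule removes them. Presumed cures not seen in the window become indeterminate and leave. Nor do the documents describe CE as the protocol-adherent analysis on which the non-inferiority claim rests.

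The reply does not settle the point. Protocol 13.1 requires an assessment in the window, and SAP section 6 says that the SAP makes no change to the protocol's analyses, which supports the literal reading. SAP 2.6 contains no sentence on carried-forward failures, earlier deaths or rescue. The carry-forward rules for EOT failure cover global and Investigator clinical response, with no matching EOT rule for mycology or radiology, so the component route remains open.

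**Conclusion.** The point holds as an unresolved rule that can bias CE, not as a demonstrated bias. Its size depends on the reading. The window and antifungal clauses have no effect if carried-forward failures and deaths stay in and rescue is not confounding. If 25%, 50% or 75% of failures are excluded equally in both arms, a true 20-point deficit appears as 18.5, 15.7 or 10.3 points. Those shares are assumptions, and unequal loss could push the difference either way. The loss of definite failures through an indeterminate component exists on both readings, but the documents do not allow it to be sized.

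A reader might infer that the EMA conclusion itself is at risk. It is not: the primary analysis is in mITT, where death, rescue, AE discontinuation and missing data all count as non-cure. What is at stake is whether the third EMA sensitivity analysis can be interpreted. That justifies a change, since two programmers could follow the present text and obtain different CE results.

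**What to change.** Make three changes in SAP 2.6:

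1. State that subjects whose Day 14 global response is failure because of death, rescue therapy, AE discontinuation or EOT failure before Day 13 are included in CE as failures, regardless of the window or an indeterminate component, if they meet the other CE criteria.
2. Limit the confounding-antifungal exclusion to systemic antifungals given for reasons other than failure of study drug.
3. Tabulate CE exclusions by reason and treatment arm, in addition to the by-subject listing in SAP 4.1.1.

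The cost is two sentences and one table, with no new data. The rule should be in place before population membership is finalized, which SAP 4.1.1 sets ahead of database lock and unblinding. The downside is that CE cure rates will be lower than under the literal reading: at 70% mITT cure and an assumed 50% exclusion of failures, 70.0% instead of 82.4%.
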